### ***Observation period***

The observation period will be divided into 3 segments:

- The **pre-treatment period** is defined as the period up to first double-blind IMP administration.
- **Double-blinded (DB) period**
  - The DB on-treatment period is defined as the period from the first DB IMP administration to the last DB IMP administration + 1 day for participants who did not enter the OL period or to the first OL IMP (the first OL visit is the nominal protocol visit Week 25) for participants who entered the OL period.
  - The DB post-treatment period is defined as the period after the DB on-treatment period for participants who did not enter the OL period.
- **Open-Label (OL) period**
  - The OL on-treatment period is defined as the period from the end of the DB on-treatment period to the last OL IMP administration + 1 day for participants who did not enter the LTE period or to the first OL IMP during the LTE (the first LTE visit is the nominal protocol visit Week 53) for participants who entered the LTE period.
  - The OL post-treatment period is defined as the period after the OL on-treatment period for participants who did not enter the LTE period.
- **Long-term extension (LTE)**
  - The LTE on-treatment period is defined as the period from the end of OL on-treatment period to the last IMP administration + 1 day.

- The LTE post-treatment period is defined as the period after the LTE on-treatment period to the end of study.

Note: Per protocol, the end of study visit occurs 4 weeks post last dose of IMP during the DB, OL or LTE period, whichever later.

Events occurred after the first double-blind IMP administration are considered treatment emergent, including on- and post-treatment events, as defined above. That is, **double-blind treatment-emergent period** includes double-blind on- and post-treatment period. **Open label treatment-emergent period** and **LTE treatment-emergent period** are defined similarly. For rilzabrutinib safety population, the entire treatment-emergent period will start from the 1st administration of rilzabrutinib.

For safety analysis, the 12-week double-blind treatment emergent period is the double-blind treatment emergent period for those discontinued before Week 13 (Day 85) or the period from the first double-blinded IMP administration to the visit date of Week 13 otherwise.

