## 3 STATISTICAL ANALYSES

### 3.1 GENERAL CONSIDERATIONS

In general, continuous data will be summarized using the number of observations available, mean, standard deviation (SD), median, (Q1 and Q3 as needed), minimum, and maximum. Categorical and ordinal data will be summarized using the count and percentage of participants.

The baseline value is defined as the last available value before the first dose of double-blind investigational medicinal product (IMP). For participants randomized but not treated, the baseline value is defined as the last available value before randomization.

The baseline value of platelet count is defined as the average of a patient's three platelet counts before the first dose of double-blind IMP: the two qualifying platelet counts at screening collected in eCRF and the platelet count at Week 1 (Study day 1).

Note: Platelet counts conducted locally will be used for efficacy analyses. Platelet counts conducted centrally will be used as a back-up for missed or non-analyzable local lab samples.

Unless otherwise specified,

- Analyses will be performed separately for adult and pediatric populations.
- Analyses will be performed by intervention group (and overall for baseline and demographics characteristics) during the double-blind period.
- Analyses will be performed in the participants who have been exposed to rilzabrutinib during each respective period for OL and LTE. Please refer to [Section 2](#), [Section 3.6](#), [Section 3.6.2](#), [Section 3.6.3](#).
- Cumulative safety analyses across periods will be based on rilzabrutinib safety population. Please refer to [Section 2](#), [Section 3.6](#), [Section 3.6.2](#), [Section 3.6.3](#).
- Limited analyses will be provided during the initial 12 weeks of double-blind treatment period before participants cross over to open-label period to have a full safety profile (see [Table 7](#)).

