a Will include the following AE categories: any AEs, any serious AEs, any AEs leading to death, any AEs leading to permanent intervention discontinuation.

b Selection criteria in [Table 8](#).

c Covid-19 related AEs identified by narrow search of SMQ = COVID-19, #20000237.

d Cumulative data from 1st dose of rilzabrutinib during OL period. Adult and pediatric populations separately.

e Cumulative data from 1st dose of rilzabrutinib during LTE period. Adult and pediatric populations separately.

f Cumulative data from 1st dose of rilzabrutinib regardless of period. Adult and pediatric populations separately.

g Including number (percent) of participants with events, number of events and event rate per participant-years of exposure.

DB = double-blind period ; OL = open-label period ; LTE = long-term extension. 12W = 12-week double-blind period ; 24W = 24-week double-blind period;

AE = adverse event ; TEAE = treatment emergent adverse event ; SAE = serious adverse event ; AESI = adverse event of special interest ; GI = gastrointestinal.

SOC = system organ class ; HLT = high level term ; PT = preferred term. CTCAE = common terminology for adverse events.

CS = corticosteroids ; TPO-RA = Thrombopoietin receptor agonist ; CMQ = Customized MedDRA query; SMQ = Standardized MedDRA query.

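### The SAP's 12-week double-blind safety period is not capped at Week 13 for participants who stop early, so last doses on Days 58 to 84 bring off-drug follow-up past Day 85 into the 12-week adverse-event tables

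*SAP*

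**What the plan says.** The definitions are all in SAP 3.1, under Observation period.

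- **Participants who stop before Week 13.** For safety analysis, "the 12-week double-blind treatment emergent period is the double-blind treatment emergent period for those discontinued before Week 13 (Day 85". No limit at Day 85 is attached.
- **All others.** Their window is "the period from the first double-blinded IMP administration to the visit date of Week 13 otherwise".
- **What the double-blind treatment-emergent period contains.** It "includes double-blind on- and post-treatment period".
- **On-treatment part.** It runs "to the last DB IMP administration + 1 day for participants who did not enter the OL period", or to the first open-label dose for those who do enter.
- **Post-treatment part.** "The DB post-treatment period is defined as the period after the DB on-treatment period for participants who did not enter the OL period". No end day is given, but the SAP notes that "the end of study visit occurs 4 weeks post last dose of IMP during the DB, OL or LTE period, whichever later".

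The purpose is stated earlier in SAP 3.1: "Limited analyses will be provided during the initial 12 weeks of double-blind treatment period before participants cross over to open-label period". Table 7 reports this window in its DB 12W columns, and the footnote expands the label as "12W = 12-week double-blind period". Neither SAP 3.6.2 nor Table 7 and its footnotes add a cap.

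**The concern.** The label and the stated purpose both promise the first 12 weeks of blinded treatment. For participants who stop shortly before Week 13, the definition delivers something longer that includes time off drug. One day's difference in the last dose changes the counting rule: a stop on Day 84 brings in four weeks of follow-up, whereas a participant who reaches the Week 13 visit is cut there.

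This is not a uniform residual-effect window. Under the protocol, a Week 13 non-responder may leave the study and then also has an end-of-study visit 4 weeks after the last dose. That follow-up is left out of the 12-week table, while the same follow-up for someone who stopped just earlier is counted.

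The DB 12W columns are the only adverse-event tables restricted to the initial 12 weeks. They report participants with at least one event, with no adjustment for length of follow-up. A window that depends on when a person stops could shift those percentages without any drug effect if the arms differ in stopping just before Week 13.

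**Working it through.** **Inputs**

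- Day of the Week n visit: 1 + 7 × (n − 1) (SAP Table 12).
- End-of-study visit: 4 weeks after the last dose (SAP 3.1; protocol Table 1 footnote x), with a ±3-day visit window (protocol Table 2).
- Adverse events are collected to each participant's end of study (protocol 9.3.1), so off-drug events are available to be counted.
- Table 7 counts participants with at least one event (SAP 3.6.2).

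**Reproducing the plan's days**

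- Week 13: 1 + 7 × 12 = Day 85, as the SAP states.
- Four weeks as 28 days: Week 53 is Day 365, and 365 + 28 = 393, the end-of-study day in protocol Table 2.

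**Window end for a participant who stops before Week 13 and does not enter open label**

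Nominal end = last dose day + 28. Overrun = end − 85, if positive.

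| Last dose | Nominal end | Days past Day 85 |
|---|---|---|
| Day 57 | Day 85 | 0 |
| Day 58 | Day 86 | 1 |
| Day 70 | Day 98 | 13 |
| Day 77 | Day 105 | 20 |
| Day 84 | Day 112 | 27 |

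With the ±3-day window, the last row ends on Days 109 to 115, against Days 82 to 88 for a participant cut at the Week 13 visit. On nominal days the excess is 27/85 = 32%. With a last dose on or before Day 57, the nominal window does not pass Day 85.

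**Size in the table**

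The documents do not say how many participants stop on these days or how often events occur, so both are assumed: 3-8% of an arm stopping on Days 57 to 84, and 3-10% per week for events.

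- Mean overrun over last doses on Days 57 to 84: (0 + 27)/2 = 13.5 days, or 13.5/7 = 1.93 weeks.
- Extra events per 100 participants = 100 × share stopping × 1.93 × weekly rate.
- Low end: 100 × 0.03 × 1.93 × 0.03 = 0.17.
- High end: 100 × 0.08 × 1.93 × 0.10 = 1.54.

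These are expected events. A participant who already has an event in a given row does not change that row by having another. So 0.2 to 1.5 per 100 is an upper bound on the participants per arm who newly have an event.

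For the planned 20 and 10 children, the same bound is 0.03 to 0.31 and 0.02 to 0.15 participants. If one child did newly have an event, the arm's percentage would move by 1/20 = 5 or 1/10 = 10 points.

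**The case against.** The strongest defence is that the rule is a stated choice. SAP 3.1 defines every treatment-emergent period, whether double-blind, open-label or extension, as on-treatment plus post-treatment. Applying that to early stoppers keeps delayed or worsening events attached to the stop. Safety analyses are descriptive, no test is planned, and every event concerned also appears in the DB 24W tables.

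The last part stands and limits the importance of the point. The first part does not rescue the definition: the convention is dropped for a participant who leaves the study at the Week 13 visit, and the result does not fit the purpose the SAP gives for these tables.

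A further objection also stands. Participants who stop much earlier have a shorter window under either rule. A last dose on Day 28 is followed to about Day 56. A cap therefore does not give everyone the same follow-up.

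A reader might also infer that the 12-week columns are the only safety comparison made before non-responders cross over. The documents do not support that. SAP 3.1 ends the double-blind on-treatment period at the first open-label dose for anyone who enters open label, so the DB 24W columns are pre-crossover as well. Table 7 footnote g adds event rates per participant-year to the DB 24W table of all events by system organ class and preferred term.

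**Conclusion.** The point holds as a small inconsistency of definition. For participants who do not enter open label, last doses on Days 58 to 84 are counted 1 to 27 days past Day 85. All others, including Week 13 non-responders who leave the study, are cut at the Week 13 visit. The overrun is the normal result of stopping in those weeks, because the protocol's routes into open label begin at Week 13. Day 112 rests on the scheduled end-of-study visit, since the SAP sets no hard end to the post-treatment period.

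Only the descriptive DB 12W tables are affected. No efficacy test, alpha or sample size changes. The bound of 0.2 to 1.5 participants per 100 in an arm depends wholly on the assumed stopping shares and event rates.

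A reader might go further and infer a bias between the arms, or events driven by new ITP treatment started after stopping. Neither is established. SAP 3.2.3.2 expects high dropout, particularly on placebo, but this concerns completion of 24 weeks and says nothing about stops on Days 58 to 84. The documents also do not say what treatment follows a stop.

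**What to change.** In SAP 3.1, end the 12-week double-blind treatment-emergent period for every participant at the earliest of:

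- the Week 13 visit date, or Day 85 if there is no such visit;
- the first open-label dose;
- the end of the double-blind treatment-emergent period.

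Keep later events of early stoppers in the DB 24W columns, where the present definitions already place them. The cost is one sentence in the SAP and a date cap in the adverse-event derivation, and no event is lost. The cap removes the overrun only, so a table footnote should say that participants who stop early still contribute shorter windows.

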### 3.2 PRIMARY ENDPOINT(S) ANALYSIS

The efficacy analyses will be based on each on-treatment period for DB, OL and LTE respectively, unless otherwise specified.

#### 3.2.1 Definition of endpoint(s)

Please refer to [Section 1.2.2.1](#) for primary efficacy endpoint.

To qualify for a durable responder (Definition 1, [Section 1.2.2.1](#)), a participant must have met ALL of the following criteria:

- At least 8 non-missing weekly platelet measurements during the last 12 weeks of the 24-week treatment period, and
- Platelet counts  $\geq 50,000/\mu\text{L}$  for  $\geq$ two-thirds of the 8 non-missing weekly assessments above, and
- At least 2 platelet counts  $\geq 50,000/\mu\text{L}$  occurred during the last 6 weeks of the 24-week treatment period, and
- Not rescued after 8 weeks of treatment and before Week 25 (or last IMP intake, whichever earlier). A participant who is rescued during this period will be considered as a non-responder, and
- Not discontinued before Week 25 due to related TEAE (per investigator's assessment) or lack of response. A participant who discontinues before Week 25 and the reason for discontinuation is treatment related adverse event (AE) or lack of response will be considered as a non-responder.

## Country-specific definition [countries within the EU (EEA countries) and UK]

To qualify for a durable responder (Definition 2, [Section 1.2.2.1](#)), a participant must have met ALL of the following criteria:

- Platelet counts  $\geq 50,000/\mu\text{L}$  for at least 8 out of the last 12 weeks [Week 14 (Day 92) to Week 25 (Day 169)] during the 24-week double-blind treatment period, and
- Not rescued after 8 weeks of treatment and before Week 25 (or last IMP intake, whichever earlier). A participant who is rescued during this period will be considered as a non-responder, and,
- Not discontinued before Week 25 due to related TEAE (per investigator's assessment) or lack of response. A participant who discontinues before Week 25 and the reason for discontinuation is treatment related AE or lack of response will be considered as a non-responder.

### 3.2.2 Main analytical approach

The main analysis of the primary endpoint is to compare the responder rate of the rilzabrutinib treatment group with the placebo treatment group via the primary estimand as defined in [Table 2](#).

To reject the null hypothesis of no treatment difference, the two-sided p-value based on a Cochran-Mantel-Haenszel (CMH) test adjusted by randomization stratification factors ([Section 3.1](#)) must be  $<0.05$  in the adult ITT population. The Mantel-Haenszel estimate of common risk difference in response rates and its associated 95% confidence interval based on Mantel-Haenszel stratum weights (1) and the Sato variance estimator (2) will be reported. The observed response rate for each treatment group will be presented along with its associated 95% asymptotic confidence interval (CI).

For pediatric participants, the observed response rate will be calculated along with its associated (90% and 95%, respectively) CI in each treatment group using the Clopper-Pearson exact method. The difference in response rate and its associated 95% exact CI will be presented.

For Pharmaceuticals and Medical Devices Agency (PMDA) in Japan, the consistency of efficacy in pediatric population will be assessed with Method 2: the difference in response rate in the pediatric population is in the same direction as that in the adult population (ie, the response rate in rilzabrutinib group is numerically higher than that in the placebo group in the pediatric population) given that the treatment effect in adults is significant (ie,  $p\text{ value} < 0.05$ ).

Graphical presentations of the results will be provided as needed. SAS® sample code could be found in [Section 5.7](#).

**Intercurrent events** will be handled with the primary estimand specified in [Table 2](#). Specifically,

1. Rescue medication: participants will be considered as non-responders if taking rescue medication after 8 weeks of double-blind treatment and before Week 25 (or last IMP intake, whichever earlier) (composite strategy).

2. Discontinuation of study intervention before Week 25 due to lack of response or related AE (per investigator's assessment in eCRF): participants will be considered as non-responders (composite strategy).
3. Discontinuation of study intervention before Week 25 due to reasons other than the aforementioned: data during the double-blind on-treatment period will be included in the analysis. Post-treatment data will be considered to have had no platelet response (composite strategy).

Note: per protocol, the end of study visit is performed at 4-week post-dose follow up where participants will have their final assessment (weekly post-dose platelet assessment not required starting from amended protocol 03).

**Missing data** will be handled as followed,

For durable platelet response Definition 2 ([Section 1.2.2.1](#)), missing data will be handled as follows,

- Missing data due to Covid-19 (per eCRF) are assumed missing at random and will be imputed using the participant's median value of available weekly platelet counts (a minimum of 3 available weekly platelet counts required) during the last 12 weeks of double-blind on-treatment period.
- Otherwise, missing data will be considered as no response. That is, if no platelet measurement is available at a specific weekly visit, that week will be considered to have had no platelet response.

[Table 4](#) in [Section 3.2.3](#) outlines assumption of missing data and its handling for each type of analyses - main analyses ([Section 3.2.2](#)) and sensitivity analyses ([Section 3.2.3](#)) of the primary efficacy endpoint.

The n (%) of participants with missing data during the last 12 weeks of the 24-week double-blind period will be summarized as follows,

- Any missing weekly platelet counts.
  - Due to any reasons,
  - Due to Covid-19,
- Number of missing weekly platelet counts: 1 to 2, 3 to 4, >4,
  - Due to any reasons,
  - Due to Covid-19.

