# 1 INTRODUCTION

## 1.1 STUDY DESIGN

This is a Phase 3, multicenter, randomized, double-blind, placebo-controlled, parallel-group study with an open-label extension.

After screening (up to 4 weeks), participants who met the eligibility criteria will be centrally randomized via Interactive Response Technology (IRT) in a 2:1 allocation ratio to 1 of 2 intervention groups: rilzabrutinib 400 mg twice daily (bid/BID) or placebo. The randomization will be carried out separately for the two age groups. For the adult group, stratified permuted block randomization will be implemented; for the pediatric group, dynamic randomization algorithm (minimization) will be implemented. The randomization will be stratified by splenectomy status (yes/no) and by severity of thrombocytopenia (Inclusion Criteria 3 platelet counts  $<15,000/\mu\text{L}$  or  $\geq 15,000/\mu\text{L}$ ).

After randomization, participants will start a Double-Blinded (DB) Treatment period of up to 24 weeks followed by an Open-Label (OL) Period of 28 weeks during which all participants will receive rilzabrutinib, and then a 4-week safety follow-up period after the last dose. Participants who respond per the criteria specified in the protocol at the end of the OL Period will be able to enter Long-Term Extension (LTE) where they will continue to receive treatment until the time expected for the last participant who enters the LTE to complete 12 months.

Approximately 224 participants (194 adults and 30 pediatric participants) will be randomized from approximately 150 sites.

Study primary analyses will be conducted when the last adult participant has concluded the blinded treatment period (see details in [Section 3.8](#)).

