### 3.2.3.2 Sensitivity Analyses – modified primary estimand – Adults in mITT, 24-week completer, participants not receiving Covid-19 vaccine (for Definition 1 and Definition 2, respectively)

Sensitivity analyses in adults will be performed to assess respectively, the potential impact of,

- Non-IMP exposure by including participants who have been randomized and exposed (ie, mITT)
- The premature discontinuation by including participants who have completed the 24-week double-blind treatment period without rescue medication (ie, 24-week completer).
- The Covid-19 vaccine by including participants who did not receive Covid-19 vaccine during the last 16 weeks of the double-blind treatment period.

Each sensitivity analysis will be carried out via a modified primary estimand, which is the same as the primary estimand defined in the main analytic approach, except for the analysis population. The same analysis as specified in [Section 3.2.2](#) will be performed ([Table 4](#)).

For the analysis in the 24-week completer, the treatment difference will likely be estimated via normal approximation without being adjusted by stratification factors due to the expected high dropout particularly in the placebo group. The analysis method and stratification factors will be specified in the footnote of the corresponding outputs.

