### **3.2.4 Subgroup analyses**

To assess the homogeneity of the treatment effect across various subgroups, analyses will be performed on the primary endpoint (Definition 1 and Definition 2 respectively) in the adult ITT population across the following subgroups (categories with fewer than 5 participants may be combined with other categories):

- Race (White, Asian, Other)
- Age group (<65 years, ≥65 years)
- Sex (Male, Female)
- Duration of ITP since diagnosis (≤1 year, >1 year to ≤3 years, >3 years)
- Prior splenectomy status (yes, no)
- Baseline platelet counts (<15,000/μL, ≥15,000/μL)
- Prior CS (No prior CS, Prior CS and no concomitant CS, Prior and concomitant CS, Prior CS and concomitant CS and TPO-RA)
- Prior TPO-RA (No prior TPO-RA, Prior TPO-RA and no concomitant TPO-RA, Prior and concomitant TPO-RA, Prior TPO-RA and concomitant TOP-RA and CS)
- Prior intravenous immunoglobulin (IVIg) or anti-D immunoglobulin (Yes, No)
- Prior rituximab (Yes, No)
- Concomitant ITP medications (Yes, No)
- Concomitant ITP medications (CS, TPO-RA, both CS and TPO-RA, neither CS nor TPO-RA)
- US vs. Non-US
- Geographic region:
  - Asia/Pacific (Australia, China, Japan, Singapore, South Korea, Thailand),

- West Europe (Austria, France, Germany, Italy, Norway, Spain, United Kingdom, Netherlands),
- East Europe (Hungary, Israel, Poland, Russia, Turkey, Ukraine),
- North America (Canada, United States),
- South America (Argentina, Brazil, Chile, Mexico).

The observed response rate will be presented along with its associated 95% asymptotic CI in each treatment group and each subgroup. The treatment difference in response rates and its associated 95% CI will be summarized for the subgroups defined above. The treatment difference for each subgroup will likely be estimated via normal approximation without being adjusted by stratification factors due to the expected small cell size. The Mantel-Haenszel estimate of common treatment difference and associated 95% ([Section 3.2.2](#)) adjusted by stratification factors may be considered if appropriate. The analysis method and stratification factors will be specified in the footnote of the corresponding outputs. The consistency of the treatment difference among these sub-populations will be examined by the forest plot.

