## 4 SAMPLE SIZE DETERMINATION

A sample size of approximately 194 (129 versus 65 adult participants in the rilzabrutinib versus placebo arms, respectively) will provide 95% power to detect a 20% difference in response rates as defined in the primary endpoint ([Section 1.2.2.1](#)) between the 2 arms (25% vs 5%, in the rilzabrutinib versus placebo arms, respectively), using the Fisher's Exact test with a 0.05 two-sided significance level.

The assumption of a 25% response rate in the rilzabrutinib group is based on the Phase 2 study PRN1008-010 Part A (DFI17124 Part A) (durable response [8 out of the last 12 weeks with platelet count at or above 50,000/ $\mu$ L in the absence of rescue medication]) and the 5% response rate is estimated based on the observed placebo response in previous randomized controlled trials of ITP medications ([11](#)). The participants who are not evaluable for primary efficacy due to dropout or missing data will be considered as non-responders.

The pediatric sample size of 30 participants (20 participants on rilzabrutinib and 10 on placebo) was determined based on clinical practice and is adequate to descriptively describe the safety and efficacy in pediatric participants. With a sample size of 20 pediatric participants on rilzabrutinib the maximum width of an exact 90% CI on response rate would be 40%.

Calculations were made based on 2-sample Exact test using SAS® 9.4.

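### The asymptotic 95% interval for adult response rates is not named; read as Wald, it covers the planned 5% placebo rate about 84% of the time at n = 65 and far less often in small subgroups

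*SAP*

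**What the plan says.** - **Adult arm rates (SAP 3.2.2):** "The observed response rate for each treatment group will be presented along with its associated 95% asymptotic confidence interval (CI"). No variant is named, and the sample code in SAP 5.7.1 requests no interval for a single arm's rate that would settle it.
- **Main adult comparison (SAP 3.2.2):** a CMH test decides, and the reported effect is the Mantel-Haenszel risk difference with the Sato variance.
- **Pediatric rates (SAP 3.2.2):** Clopper-Pearson intervals for each arm and an exact interval for the difference.
- **Subgroups (SAP 3.2.4):** each subgroup arm again gets an asymptotic interval. The difference "will likely be estimated via normal approximation without being adjusted by stratification factors due to the expected small cell size". A stratified Mantel-Haenszel estimate may be considered instead. Categories with fewer than 5 participants may be pooled. Consistency is examined on a forest plot.
- **24-week completers (SAP 3.2.3.2):** the difference "will likely be estimated via normal approximation without being adjusted by stratification factors due to the expected high dropout", which is expected to be highest on placebo.
- **Stable response (SAP 3.3.2.1):** the interval for the proportion also uses a normal approximation.
- **Planning assumptions (SAP 4):** "25% vs 5%, in the rilzabrutinib versus placebo arms, respectively", in "129 versus 65 adult participants in the rilzabrutinib versus placebo arms, respectively".

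**The concern.** With 65 placebo adults and a 5% rate, 65 × 0.05 = 3.25 responders are expected. This is where the Wald interval performs badly: it is symmetric about a small proportion, can run below zero, and has zero width when nobody responds. Subgroup arms and placebo completers will be smaller still. Children get exact intervals in the same section; adults do not.

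At stake is how the published placebo rate and the forest plot are read. SAP 3.8 makes the adult early analysis final and the basis for registration. A placebo bar of 0% to 0%, or a subgroup difference that appears to exclude zero only because the placebo arm adds no variance, would mislead a reader.

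**Working it through.** **Inputs.** From SAP 4: 129 and 65 adults, 25% and 5%. From SAP 1.1: randomization "in a 2:1 allocation ratio to 1 of 2 intervention groups". The documents give no subgroup sizes, so the sizes below are assumptions that keep the 2:1 ratio.

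**The plan's own figure.** SAP 4 says the sample "will provide 95% power to detect a 20% difference in response rates", "using the Fisher's Exact test with a 0.05 two-sided significance level". Enumerating both binomials gives 96.4%, consistent with the stated 95%, so the planning inputs are read correctly.

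**Placebo arm, n = 65.** The Wald interval is p ± 1.96 × √(p(1 − p)/n). At 3/65, p = 0.046 and the half-width is 1.96 × √(0.046 × 0.954/65) = 0.051.

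| Responders | Wald | Wilson | Clopper-Pearson |
|---|---|---|---|
| 3/65 | −0.5% to 9.7% | 1.6% to 12.7% | 1.0% to 12.9% |
| 0/65 | 0% to 0% | 0% to 5.6% | 0% to 5.5% |

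Coverage at a true 5%, by exact enumeration, is 83.7% (Wald), 95.7% (Wilson) and 98.4% (Clopper-Pearson). The Wald misses are one-sided: the upper limit is too low in 15.8% of trials and the lower limit too high in 0.5%. The 15.8% comes from 0 or 1 responders, where the upper limits are 0% and 4.5%: 0.95^65 + 65 × 0.05 × 0.95^64 = 0.036 + 0.122 = 0.158.

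**Smaller placebo groups, true rate 5%.** The chance of a zero-width interval is 0.95^n.

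| Placebo n | Wald coverage | P(interval is 0% to 0%) |
|---|---|---|
| 65 | 83.7% | 3.6% |
| 20 (assumed) | 63.9% | 36% |
| 10 (assumed) | 40.0% | 60% |
| 5 (assumed) | 22.5% | 77% |

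**Rilzabrutinib arm.** Wald coverage at 25% with n = 129 is 94.5%, which is adequate.

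**Unadjusted differences, 25% vs 5%.** Wald is d ± 1.96 × √(p₁(1 − p₁)/n₁ + p₀(1 − p₀)/n₀). Newcombe combines the two Wilson intervals.

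| n₁/n₀ (all but the first assumed) | Wald coverage | Newcombe coverage |
|---|---|---|
| 129/65 | 94.5% | 95.7% |
| 60/30 | 95.2% | 96.2% |
| 40/20 | 93.2% | 96.4% |
| 20/10 | 94.3% | 97.6% |
| 10/5 | 92.4% | 98.2% |
| 4/2 | 63.6% | 96.8% |

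Two-sided coverage therefore holds up except in the tiniest categories.

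**Unadjusted differences, no true effect.** The table gives the probability that the lower limit exceeds zero (nominal 2.5%), by exact enumeration.

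| n₁/n₀ | Rate in both arms | Wald | Newcombe |
|---|---|---|---|
| 129/65 | 5% | 5.9% | 1.1% |
| 60/30 | 5% | 7.7% | 0.2% |
| 20/10 | 15% | 7.1% | 0.4% |
| 20/10 | 5% | 1.0% | 0.0% |

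The excess is real in several settings but not universal.

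**Example, 5/20 vs 0/10.** The placebo variance term is 0, so the Wald half-width is 1.96 × √(0.25 × 0.75/20) = 0.190 and the interval is +6.0% to +44.0%. Newcombe gives −6.0% to +46.9%. Only the first excludes zero.

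**The case against.** The strongest reply has four parts.

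- **Asymptotic need not mean Wald.** Wilson is asymptotic too and does not collapse. This stands: for arm rates the 84% rests on the usual reading, and strictly the SAP is under-specified. That is still a reason to name the interval. For the differences, a normal approximation is most naturally Wald.
- **No decision depends on these intervals.** The CMH test carries the primary conclusion. Subgroups have no decision rule and lie outside the multiplicity scheme in SAP 3.5. This stands.
- **The SAP leaves room.** Very small categories may be pooled, a stratified estimate may be considered, and the method will be footnoted. This softens the point. But a category of 5 can still stand alone, and a footnote does not repair an interval.
- **Difference coverage is near nominal at the planned rates.** This also stands, down to about 10 vs 5. What remains is the excess of positive lower limits when there is no effect.

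A reader might also infer more than the documents support:

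- *That the intervals are far too narrow.* At 3/65 the Wald width is 10.2 points against 11.1 (Wilson) and 11.9 (Clopper-Pearson). The fault there is mainly location.
- *That difference intervals collapse when placebo has no responders.* In practice both arms need 0 responders: 0.2% of cases at 20/10 and 4.4% at 10/5, at 25% vs 5%.
- *That the SAP chose the normal approximation because cells are small.* The wording more naturally gives small cells as the reason for dropping stratification.
- *That a high rate of excluding zero at 25% vs 5% shows error.* At 20/10 it is 50% with Wald and 13% with Newcombe, but a true effect exists there. Those figures are power.

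**Conclusion.** The concern holds as a reporting defect. If the adult arm interval is Wald, the nominal 95% interval for the placebo rate has about 84% coverage at the planned 5%. Small placebo subgroups do much worse, and zero-width bars are likely there. Unadjusted difference intervals are acceptable on two-sided coverage at the planned rates. With no effect, they point to benefit up to about three times as often as they should in some settings (7.7% against 2.5%).

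The result assumes the Wald reading, the planned rates and illustrative subgroup sizes. If placebo response is lower, coverage is worse (72.9% at a true 2%); at 10% it is 88.9%.

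The primary conclusion is not in question. The CMH p-value does not use these intervals. The Mantel-Haenszel/Sato interval covered 94.6% to 94.7% in simulations at 25% vs 5% under two assumed splits over four strata.

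**What to change.** - In SAP 3.2.2 and 3.2.4, specify Wilson or Clopper-Pearson intervals for adult arm and subgroup response rates. Do the same for the stable-response proportion in SAP 3.3.2.1.
- In SAP 3.2.4 and 3.2.3.2, specify Newcombe or Miettinen-Nurminen intervals for unadjusted subgroup and completer differences.
- Keep the CMH test and the Mantel-Haenszel/Sato difference as they are.

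The cost is a sentence in each section and a procedure option, with no new data. The intervals become somewhat wider and can be conservative in very small subgroups: Newcombe covers 98.2% at 10 vs 5.
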